- Which parts of the program (which gathering) were most helpful?
- Which parts of the program (which gathering) was least helpful?
- What would you change to make the program better for the future?
 - What would you add?
 - What would you get rid of?
- Since starting with the Báa nnilah program, what other support in addition to being in the program has made a difference for your health?
- What changes have you noticed in the community as a result of this program?
- What do you see for your health for the future?
- What information/tips/techniques from the program will you use in the future?

- What ideas do you have for the future of the Ba nnilah program in the Crow community?

Aho. Thank you for your time today. You are helping us to make the Ba nnilah program most effective.

3. Intervention facilitators interview protocol.

Mentor Qualitative Interview Questions

Mentor: _____

Date: _____ Time: _____

Location: _____

Hello, I am [name]. Thank you for taking the time to visit with me today. We would like to learn about your experience as a Mentor in the Báa nnilah program. This will help us understand how to improve the program in the future. If it's ok with you, I would like to record our conversation so I don't miss anything that you're sharing. Do you have any questions before we get started?

1. What does being a Mentor mean to you?
2. What experiences did you have before your involvement in the Báa nnilah program that helped prepare you for being a Mentor?
3. How did you prepare for your gatherings?
4. How did you feel leading the first gathering of your first group compared to leading the first gathering of your second group?
5. Think back to a time when you were feeling the most comfortable leading your gathering. What made you feel that way?
6. Think back to a time when you were feeling the most confident leading your gathering. What made you feel that way?
7. How did you personalize your gatherings to make them your own?
8. How did you know that participants understood or didn't understand the gathering material?
9. Can you tell me about the support that you received from program staff (i.e, [name], [name], [name], [name], and the Bozeman team)?
 - a. What worked well for you?
 - b. What didn't work well for you?
10. How was it for you when program staff attended your gathering(s)?
 - a. How did that support you or not support you as a Mentor?
11. What other ways can program staff support you as a Mentor?
12. What does successful mentorship look like to you?

Aho. Thank you for your time today. You are helping us make the Báa nnilah program better.

**Montana State University
Institutional Review Board
Request for Minor Modifications/Amendments**

Instructions: E-mail completed form and all revised and/or new study documents to:
[contact]

Note: The project's IRB-approved Research Protocol must be kept current and followed throughout the life of the project with yearly renewals. Protocols approved in the Exempt category do not require yearly renewals. All study documents are subject to review.

- 1. IRB approval number:** SH082017
- 2. Project Title:** Improving chronic illness management with the Apsaalooke Nation: The Ba nnilah project
- 3. Principal Investigator:** [name]
Contact information (phone/e-mail): [name] / [contact]
Address (where you want approval letter sent):

- 4. Requesting modification/amendment to:**
 Research protocol
 Consent form
 Recruitment materials
 Survey instrument, interview questions
 Research personnel
 Other, please explain:

- 5. Describe the modification being requested:**
Note: with each requested change, provide a detailed description of where within the study documents (e.g. Research protocol, survey instrument, etc.) the changes are reflected (e.g., section, question #, etc.).

We have made slight wording changes to reflect a less stringent timeline of follow-up.

- 6. Have these requested changes been initiated?**
 No
 Yes
- 7. How will the proposed modification(s) affect study participants?**
Study participants indicating higher levels of depression symptoms and/or more frequent suicidal thinking during study assessments will still be followed-up by community project leaders ([name] and [name]) but with a less stringent timeline than previously indicated.

**Montana State University
Institutional Review Board
Request for Minor Modifications/Amendments**

Instructions: E-mail completed form and all revised and/or new study documents to:
[contact]

Note: The project's IRB-approved Research Protocol must be kept current and followed throughout the life of the project with yearly renewals. Protocols approved in the Exempt category do not require yearly renewals. All study documents are subject to review.

- 1. IRB approval number:** SH082017
- 2. Project Title:** Improving chronic illness management with the Apsaalooke Nation: The báa nnílöh project
- 3. Principal Investigator:** [name]
Contact information (phone/e-mail): [name]/[contact]
- 4. Requesting modification/amendment to:**

Research protocol
Consent form
Recruitment materials
 Survey instrument, interview questions
Research personnel
Other, please explain:

- 5. Describe the modification being requested:**
Note: with each requested change, provide a detailed description of where within the study documents (e.g. Research protocol, survey instrument, etc.) **the changes are reflected** (e.g., section, question #, etc.)

We would like to make amendments to our IRB application that was approved August 2017. In the application, we had three different groups of people from whom data was to be gathered.

1. Participants of intervention: all participants
2. Participants of intervention: subgroup
3. Intervention facilitators

We would like to make amendments to #1 and to introduce a new group:

4. Participants of modified intervention

1. Participants of intervention: all participants. We have completed data collection 3 times for this group, which consists of our intervention group and our wait-list control group completing the survey approved by the IRB. We would like approval to:

- Make slight modifications to some of the demographic questions to ask if the response changed since the last survey and if it did not, to skip the question. This will hopefully make the survey quicker for participants to complete.
- Remove 2 questions that should not vary over time: 1) gender and 2) year of birth.
- Add a checklist of questions to assess changes in participants since they began the program.

The original questions and changes and the checklist of questions are below.

4. Participants of modified intervention. We have run both the intervention and wait-list control group through our 7-session intervention. We would like to explore the idea of an implementation study and are also committed to sustaining the intervention, as we shared in our grant application to NIH. We have made small changes to our intervention to improve the experience for participants. For example, wording changes for clarity, adding a new handout on whole grains, switching the order of 2 of the gatherings for clarity, and changing a few of the exercises in the handouts to make it easier for all community members to engage in the exercises. This spring, we will run 2 groups of approximately 10 participants through the 7 gatherings of the intervention. We will not have them complete the survey and exercises that the intervention and wait-list control group completed. We would like permission to gather information in two areas:

- 1) Have them complete the PHQ-9 survey, which gathers information on depression. This will be given to each participant at the first gathering. We are having them complete this survey as we saw many community members with concerning scores and we have implemented a follow-up protocol with our intervention and wait-list control that we will follow with these participants.
- 2) We will have participants complete the checklist of questions that is below at the bottom of the document at the end of their participation.

6. Have these requested changes been initiated?

No
Yes

7. How will the proposed modification(s) affect study participants?

Note: Federal regulations require IRB approval prior to changing a research procedure or deviating from IRB approved documents unless it is in the best interest of or for the safety of study participants.

This will not affect study participants except the minor changes to the interview protocol.

1. Participants of intervention: all participants.

“From” is the existing format of the question. **“To”** is the revised format.

From: Which community do you live in?

To: Since the last time you took this survey, have you moved to a different community?

No: go to next question

Yes: go to choices of community

From: What is your current marital status?

To: Since the last time you took this survey, has your marital status changed?

No: go to next question

Yes: go to choices, with this difference: combine “separated” and “divorced” into one choice (“separated or divorced”); delete “single, never married” and “other” categories

From: What was the highest grade or year of school that you completed?

To: Since the last time you took this survey, have you gone back to or graduated from school?

No: go to next question

Yes: go to choices of education with these differences:

- combine: “some technical/vocational school” and “some college” into one choice “some education after high school”
- change “high school graduate or diploma” to “high school graduate or GED”

From: Employment status: select the statement that fits your situation best

To: Since the last time you took this survey, has your employment status changed?

No: go to next question

Yes: go to choices of employment status

From: Please select the number that shows how much your total household income was for the past 12 months [Household means all of the people who live with you and share income and expenses]

From: About how many miles do you travel to get to the clinic where you receive your health care?

To: About how many miles do you travel to get to the clinic where you receive most of your health care? (one way)

From: Please select the type of health insurance or health coverage that pays for your health care? (select all that apply)

To: Since the last time you took this survey, has your health insurance or health coverage changed?

No: go to next question

Yes: go to question and choices of health insurance

From: Please select the ongoing illness(es) that a doctor has told you that you have.

To: Since the last time you took this survey, has your doctor told you that you have a new ongoing illness?

No: go to next question

Yes: Please type in the new ongoing illness that you now have (include an open box)

And: Since the last time you took this survey, has your doctor told you that you no longer have an illness that you were diagnosed with before?

No: go to next question

Yes: Please type in the ongoing illness that you no longer have (include an open box)

From: do you have any additional comments you would like to add? (tap the white box below)

To: Please share what you gained or learned from the program and what changes in your health or behavior you made because of the program? (tap the white box below)

1. Participants of intervention: all participants.

4. Participants of modified intervention.

We will add this checklist: Check off all of the changes you have noticed since you started in the B nnilah program:

Eating healthier

Drinking more water

Drinking less pop or other sugary drinks

Taking more walks or exercising more

Taking my medication more regularly

Having better communication with my doctor

Having better relationships with my spouse or other family members

Feeling less alone

Lost weight

Shared information from the Báa nnilah program with others

Feeling more hopeful

Feeling less stressed

Having more support

Having more understanding that there are others going through what I am going through

Feeling more connected to my community

**Montana State University
Institutional Review Board
Request for Minor Modifications/Amendments**

Instructions: E-mail completed form and all revised and/or new study documents to:
[contact]

Note: The project's IRB-approved Research Protocol must be kept current and followed throughout the life of the project with yearly renewals. Protocols approved in the Exempt category do not require yearly renewals. All study documents are subject to review.

- 1. IRB approval number:** SH082017
- 2. Project Title:** Improving chronic illness management with the Apsaalooke Nation: The báa nnílöh project
- 3. Principal Investigator:** [name]
Contact information (phone/e-mail): [name]/[contact]
- 4. Requesting modification/amendment to:**

Research protocol
Consent form
Recruitment materials
 Survey instrument, interview questions
Research personnel
Other, please explain:

- 5. Describe the modification being requested:**
Note: with each requested change, provide a detailed description of where within the study documents (e.g. Research protocol, survey instrument, etc.) **the changes are reflected** (e.g., section, question #, etc.)

We would like to make amendments to our IRB application that was approved August 2017. In the application, we had three different groups of people from whom data was to be gathered.

1. Participants of intervention: all participants
2. Participants of intervention: subgroup
3. Intervention facilitators

We would like to make amendments to #1:

1. Participants of intervention: all participants. We have completed data collection 4 times for this group, which consists of our intervention group and our wait-list control

group completing the survey approved by the IRB. We have one more data collection event and this event is only with the wait-list control group. We would like approval to add this question:

- What do you think is the best way to for us to learn what the Ba nnilah program did for its participants, family members, and for the Crow community as a whole?
 - If they say, “a survey” or “asking people who took part” say, “please explain” or “what questions would you ask?”

6. Have these requested changes been initiated?

No

Yes

7. How will the proposed modification(s) affect study participants?

Note: Federal regulations require IRB approval prior to changing a research procedure or deviating from IRB approved documents unless it is in the best interest of or for the safety of study participants.

This will not affect study participants except the minor changes to the interview protocol.

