Participant retention: *Aakbaabaaniilea* will check in with participants via telephone on a weekly basis to remind them of upcoming intervention meetings and to problem-solve any issues. It is estimated that the current community-based leadership role of the *Aakbaabaaniilea* in the community and the relationships established through the intervention will contribute to participant retention. We will provide incentives that have worked in our past intervention research with the Apsáalooke Nation, including gas vouchers to assist with transportation to and from the intervention site and by holding a graduation at the end of the intervention where participants who complete the program will receive a larger gift incentive. Our CAB believes that the culturally consonant intervention and the long-standing partnership will be strong incentives to keep program participants engaged. In our Messengers for Health study, community members consistently attended monthly meetings for the entire intervention period, which was 5 years.

b. Sources of materials

Data will consist of:

1. Quantitative measures of: demographic information, quality of life, physical function, satisfaction with participation in social roles, satisfaction with social roles and activities, social isolation, psychosocial impact of illness, emotional distress, health care relationship trust and patient activation.
2. Qualitative data on fidelity and acceptability of the *Baa nnilah* intervention. Data that has individually identifiable private information about human subjects will be managed primarily by the PI/PDs ([name] and [name] [name]). The faculty at the Montana State University Human Ecology Learning and Problem Solving (HELPs) Lab will receive the data in order to de-identify all data before the analysis phase is initiated. The PI/PDs and faculty of the HELPS lab have undergone Collaborative IRB Training Initiative (CITI) training for human subjects research. Further, research team members will have completed a research ethics training course required by the IRBs prior to contact with potential project participants.

c. Potential risks

While there is always a possibility that participants may experience discomfort completing the measures listed above, there is a low possibility of this occurring as the result of the proposed project because Apsáalooke community members have approved all measures in advance of the study through a collaborative process.

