B.3 Procedures for protecting the confidentiality of participant data: Confidentiality of data will be maintained by the numerical coding and stripping of identifying information of all data upon transfer to MSU and the University of Nevada-Las Vegas. The MSU HELPS lab will be responsible for this action and for secure transmission of data to [name] at University of Nevada-Las Vegas. The data will be kept in the private offices of [name] and [name]. Data will be entered into tablets and the tablets will be secured in a locked cabinet at [name] office. Data from the tablets will be downloaded onto a disk and personally transported to MSU. After the study is completed, the tablets with the data files will be personally transported back to MSU by one of the PIs and secured in a locked cabinet. All subjects will be assigned ID numbers with names that will be maintained in locked and secure files by [name]. Additionally, all data will be stored in locked file drawers at each stage of data transfer. Moreover, all data obtained will be accessible only to the research staff, and no subject will be identified in any report of the project. The intervention Mentors, Project Assistant, and research assistants will be thoroughly versed in ethical issues associated with this research, with specific attention to confidentiality, and will be IRB certified by MSU. All research staff will sign a formal oath of confidentiality as part of their employment contract.

C. 1. Procedures for identifying, reviewing, and reporting adverse events and unanticipated problems to the IRB and NIH IC.

Procedures and timeline for reporting Adverse Effects to the IC

Reporting Procedure for Serious Unanticipated Adverse Events: In the event of an unanticipated serious adverse event, the project PIs will ensure that these events are reported to the IC Program Official within hours by phone, fax, and/or email and will submit a written report to the Program Official no more than two days later. The project personnel will also utilize the following reporting procedures:

1. When the research team, project personnel and /or PIs become aware of a serious adverse event, reporting requirements must be implemented in a timely manner;
2. The PIs complete an "Adverse Event Reporting Form" and submit the form to the Human Subjects Officer at MSU and LBHC;

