3. The Human Subjects Officer immediately distributes the form to the following individuals or groups as required: Division of Sponsored Research; the Data and Safety Monitoring Committee; and, the MSU and LBHC IRB Officials;
4. The Human Subjects Officer will convene an expedited meeting of the IRB. The IRB, with input from the PIs and the Data and Safety Monitoring Committee, will review the study protocol and determine what further action should be taken based on the best interests of the participants and of the research; and,
5. The PIs will report any actions taken by an IRB.

Critical problems: A protocol for identifying, reviewing, and reporting will be put into place in the event of any of the following critical problems:

1. Increased morbidity and/or mortality related to the study intervention;
2. Adverse reactions to the educational intervention;
3. Unsatisfactory performance of the study;
4. Suspicion of fraud;
5. Failure to comply with recruitment criteria; and/or
6. Any other issues that would require an important protocol change

Notification of any critical problems may be done initially through telephone but must be subsequently documented in writing either through e-mail or postal mail correspondence.

D. For multi-site studies, procedures to ensure compliance with monitoring plan and reporting requirements across study sites: This does not apply as this study is a single-site study.

E. Assessment of external factors or relevant information that may have an impact on the safety of participants or on the ethics for the research study: The Apsaalooke community-based PI, [name] will take the lead on this assessment.

F. Advanced plans for interim and/or futility analysis as appropriate: This is not appropriate.

Inclusion of Women and Minorities

1. **Describe the planned distribution of subjects by sex/gender, race, and ethnicity for the proposed study and complete the format in the Planned Enrollment Report:** Planned enrollment report is complete and in the application. There will be an estimated 100 men and 100 women who are all American Indian enrolled in the study. Additional guidance for research utilizing existing datasets: We are not using existing datasets

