We would like to make amendments to our IRB application that was approved last fall. In the application, we have three different groups of people from whom data will be gathered.

1. Participants of intervention: all participants
2. Participants of intervention: subgroup
3. Intervention facilitators

1. Participants of intervention: all participants. There are two changes – one to the timeline and one to add a data collection element.

For this group, the actual timeline for group data collection is different from what was proposed in the application. The application has data gathering events occurring in March 2018, August 2018, and December 2018 for the intervention participants. The actual months will be April/May 2018, October/November 2018, and April 2019.

We are proposing to add a data collection element for the intervention participants. All participants attend 7 gatherings as a part of the intervention. The intervention is led by facilitators who are members of the Crow community. Project staff members will send postcard reminders the week before each gathering and text or phone call reminders to participants on the day of each of the 7 gatherings. Project staff will save participant phone numbers only by participant ID number versus by name. Any responses to the text or phone reminders will be archived, again only by participant ID. Additionally, we would like to add questions to the post-intervention survey to ascertain how well each of the retention strategies helped participants to keep attending each of the gatherings (to improve and track participant retention). The questions are below and will be answered on computer tablets with the already approved surveys.

Please check how much each of the following helped you to keep coming to the gatherings

	Not at All	A Little Bit	Somewhat	Quite a Bit	Very Much
Newsletter					
Gifts received at gatherings					
Gas cards received at gatherings					
My supportive partner					
Information I learned at the gatherings					
My personal motivation					
Collecting my feathers (goals)					
Healthy meals at gatherings					
My relationship with my mentor					
My bonding with other participants					
Location of gatherings					
Postcard reminders					
Phone texts/calls from MSU team members					
Phone texts/calls from my mentor					
Other (please explain):					

Please check how much each of the following prevented you from attending the gatherings

	Not at All	A Little Bit	Somewhat	Quite a Bit	Very Much

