Participant & Environmental Factors (Ex. Health condition, weather, deaths, presence of people not in the program, etc.)					
Comments					

**Montana State University
Institutional Review Board
Request for Minor Modifications/Amendments**

Instructions: E-mail completed form and all revised and/or new study documents to:
[contact]

Note: The project's IRB-approved Research Protocol must be kept current and followed throughout the life of the project with yearly renewals. Protocols approved in the Exempt category do not require yearly renewals. All study documents are subject to review.

- 1. IRB approval number:** SH082017
- 2. Project Title:** The baa nnilah project
- 3. Principal Investigator: [name]**
Contact information (phone/e-mail): [name]/[contact]
- 4. Requesting modification/amendment to:**
 Research protocol
 Consent form
 Recruitment materials
 Survey instrument, interview questions
 Research personnel
 Other, please explain:

- 5. Describe the modification being requested:**
Note: with each requested change, provide a detailed description of where within the study documents (e.g. Research protocol, survey instrument, etc.) **the changes are reflected** (e.g., section, question #, etc.)

We would like to make amendments to our IRB application that was approved last fall. In the application, we have three different groups of people from whom data will be gathered.

1. Participants of intervention: all participants
2. Participants of intervention: subgroup
3. Intervention facilitators

1. Participants of intervention: all participants. There are three additions we would like to make to our data collection.

First addition: To gather accurate data for adverse reporting, we would like to add these questions to the computer tablets:

- ❖ Since you last took this survey have you been in a hospital overnight because of your health?

Yes/no

Since you last took this survey have you been to the emergency room because of your health?

Yes/no

Second addition: The first question below was on our original protocol to gathering information on contamination from the wait-list control group. We would like to add the second and third question.

1. The Messengers for Health Baa nnilah program consists of 7 gatherings in the local Crow communities and Hardin that are led by a community member mentor. Have you taken action for your health because of something you have heard or learned from a friend or family member who has attended the gatherings?

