Clinicaltrials.gov: Cover page

Official title of study:

Improving Chronic Illness Management With the Apsaalooke Nation: The Baa
Nnilah Project

NCT number: NCT03036189

Date of the document: 8/23/22

Statistical Analysis Plan

Statistical analysis. Statistical analyses were conducted using SAS 9.4®.³¹ Descriptive statistics were obtained for all study variables. Mean and standard deviation were calculated for continuous variables, and frequency and percentage for categorical variables. Distributions of continuous variables were examined for non-normality and outliers. Missing data patterns were examined for all variables. To compare the two study groups on baseline demographic characteristics and outcome measures, independent *t*-tests were conducted for the continuous variables, and chi-square tests for the categorical variables.

To test the main hypotheses regarding the effectiveness of the intervention and longitudinal trend on each outcome measure, a hierarchical linear modeling (HLM) approach was adopted, and each hypothesis was tested in SAS 9.4 using the *Proc Mixed* procedure. Observations were nested within individuals and individuals nested within family/clan clusters. Up to four observations (i.e., measurements over four waves of data collection) per participant in the intervention group ($n = 104$, number of clusters = 45) and up to five observations per participant in the WLC group ($n = 107$, number of clusters = 50) were obtained. All available observations were included in the analysis to test whether the outcome measure changed significantly over time (i.e., number of weeks since baseline) and whether the change significantly differed between the two study groups.) Time-invariant covariates included age at baseline, sex, study group membership, number of chronic illnesses, and number of gatherings attended. In addition, a dummy variable indicating whether each participant had attended intervention sessions at each time of data collection was included in the analytical model as a time-varying covariate. The number of valid data points varied across individuals, as well as by time and by variable within each individual, because participants could 1) miss a data collection but complete subsequent data collection(s) and/or 2) choose not to complete a physical test or a survey question. Full information maximum likelihood estimation (MLE) was used to handle missing data, which allowed us to use all available non-missing data.

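### Hospital and emergency events are asked about only as an undated yes/no at attended surveys, so a yes cannot be judged for relatedness, or timed within the programme interval or after a missed wave

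*Protocol*

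**What the plan says.** The questions come from an undated IRB amendment, under its first addition, whose stated aim is accurate adverse-event reporting. The two tablet items are "Since you last took this survey have you been in a hospital overnight because of your health" and "Since you last took this survey have you been to the emergency room because of your health". Each takes yes or no. Nothing asks when, how often or why. The second addition in the same amendment does branch: a yes on the wait-list contamination question leads to a 0 to 10 rating of extent and an open-text item.

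Baseline was set for October 2017 (Protocol, section B, Research procedures). The timeline amendment moves the follow-ups: "The actual months will be April/May 2018, October/November 2018, and April 2019". The last amendment reports four completed collections and adds: "We have one more data collection event and this event is only with the wait-list control group". The SAP gives up to four observations per participant in the intervention arm (n = 104) and up to five in the wait-list arm (n = 107). It also notes that people could skip a wave and return later.

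On reporting, section C.1 of the Data safety and monitoring plan has the principal investigators notify the funder of unanticipated serious events, after which they "will submit a written report to the Program Official no more than two days later". The listed steps begin once staff learn of an event. The first critical problem listed is "Increased morbidity and/or mortality related to the study intervention".

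Other contact is described too. Mentors "will check in with participants via telephone on a weekly basis to remind them of upcoming intervention meetings" (Participant retention). Mentors and principal investigators hold weekly safety teleconferences (section B.1). Staff contact people who drop out (Facilitator measures of fidelity, item 3). The SAP describes no analysis of the hospital or emergency items.

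**The concern.** The items are meant to support adverse-event reporting, yet a bare yes does not supply what that reporting needs. Without a reason, nobody can say whether an admission had anything to do with the programme, which the first critical problem turns on. Without a date, an event in the programme interval cannot be placed before, during or after the gatherings. Because the window starts at each person's own last survey, its length depends on attendance. Only attenders answer, so people too ill to come are missed until they return, and deaths cannot be self-reported.

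At stake is the harm side of the trial. Baseline to wave 2 is the only period in which treated and still-untreated people can be compared. Events that cannot be assigned to it weaken that comparison, and a monitoring board would have counts it could not interpret.

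**Working it through.** **1. The SAP's own wave counts.** Baseline plus three shared follow-ups = 4 observations; plus one wait-list-only wave = 5. Both match the SAP. Reporting windows are one fewer than observations: 3 in the intervention arm, 4 in the wait-list arm.

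**2. Length of the recall window.** Inputs: wave 1 October 2017, wave 2 April/May 2018, wave 3 October/November 2018, wave 4 April 2019. Central value = (mid-date of later wave − mid-date of earlier wave) / 30.44 days. The minimum runs from the end of the earlier wave to the start of the later one; the maximum runs from start to end.

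| Surveys attended | Central (months) | Range (months) |
|---|---|---|
| 1 then 2 | 6.5 | 5.0–8.0 |
| 2 then 3 | 6.0 | 4.0–8.0 |
| 3 then 4 | 5.5 | 4.0–6.9 |
| 1 then 3 (wave 2 missed) | 12.5 | 11.0–14.0 |
| 2 then 4 (wave 3 missed) | 11.5 | 10.0–12.9 |
| 1 then 4 (waves 2 and 3 missed) | 17.9 | 17.0–18.9 |

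For a wait-list member who misses wave 2, the 12.5-month window is 6.5 months of untreated wait plus 6.0 months containing the programme. One yes does not separate them.

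**3. Where a yes can be placed for someone who attends every wave.** The actual gathering dates are not restated after the timeline moved, so this assumes the designed order still held.

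| Interval | Intervention arm | Wait-list arm |
|---|---|---|
| Waves 1–2 | contains the programme: timing unknown | wholly before the programme |
| Waves 2–3 | wholly after | contains the programme: timing unknown |
| Waves 3–4 | wholly after | wholly after |
| Waves 4–5 | no survey | wholly after |

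So timing is lost in one interval per arm, and additionally wherever a boundary wave is missed.

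**4. Total follow-up by arm.** Through wave 4 both arms have the same planned 17.9 months. The date of wave 5 is not given. If it fell between July and October 2019 (an assumption), wait-list follow-up runs to 20.9–24.0 months, a ratio to the intervention arm of 20.9/17.9 = 1.17 to 24.0/17.9 = 1.34.

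**The case against.** The strongest reply is that these two items supplement the main safety route. The teleconferences are weekly and expressly about safety, the community investigator can be reached in between, mentors phone weekly, and dropouts are contacted. This stands against a reading that a reader might infer: that events reach the team only at surveys, months late. The reporting clock starts when staff become aware, so survey spacing does not contradict it. What does not stand is that these routes fill the gap. None is described as asking a hospital or emergency question, and all depend on someone mentioning the event.

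A reader might also infer that mentor calls reach only the arm in the programme. The calls are tied to gatherings, but the participant handout says waiting groups stay in contact, and each mentor recruits for both arms. Unequal detection is possible, not shown.

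Two more readings go too far. Events are not unplaceable in general: for consecutive attenders, intervals outside the programme are clear. Nor are the periods unequal by arm in the randomised comparison: waves 1 to 2, and all waves through 4, are planned alike. One could assume an admission rate and derive a spurious gap from three windows against four, but no section proposes that cumulative total. The gap would also rest on assumed rates, independent windows and an unknown wave 5 date.

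Finally, a reader might suspect that the items began after wave 2, leaving the first interval unasked. The amendment is undated. It extends a wait-list question that the survey measures assign to the first follow-up, which suggests the items were ready for wave 2 but does not settle it.

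**Conclusion.** The concern holds in a limited form. The only structured collection of hospital and emergency events is a yes/no with no date, count or reason, asked at attended waves. A yes cannot be judged for relatedness. It cannot be timed within the interval containing the programme. After one missed wave it spans about 12 months (range 10 to 14), and about 18 if only waves 1 and 4 are attended. For a wait-list member who skips wave 2, it mixes untreated wait with programme.

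The randomised comparison over waves 1 to 2 remains usable for people who attended wave 2, provided the items were in use by then. Totals over all waves would not be comparable by arm, because the wait-list arm has a fifth wave.

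This rests on the amended wave months, on the programme lying between waves as designed, and on an assumed wave 5 date for the total follow-up ratio only. The documents give no attendance by wave, so the number of affected answers is unknown. The primary outcome is untouched. This is a worthwhile, inexpensive improvement to harm reporting, not a flaw in the main analysis.

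**What to change.** Collection:

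- Keep the existing recall window. Tying it to the previous scheduled wave instead would lose events that came before a skipped wave.
- On a yes, branch to number of times, month and year, and reason, as the same amendment already does for contamination.
- Have existing staff ask the same two items by phone of anyone in either arm who misses a wave, and log known deaths.
- Pass each yes to the adverse-event review already set out in the monitoring plan. Section C.1 does not define serious or unanticipated, so the plan should state which definitions that review applies.

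Reporting:

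- Show events by arm for baseline to wave 2 as the randomised comparison, with the number in each arm who missed wave 2.
- Give longer follow-up per person-month, not as totals over three against four windows. The SAP measures time in weeks since baseline, so each person's window length should be available.
- State when the items were first used.

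The SAP is dated August 2022 and written in the past tense. If collection has closed, the reporting steps still apply.

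Cost: about a minute of survey time for those who answer yes, some calls by existing staff, one table, and dates that are only approximately recalled.
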